This is a single center, open-label, randomized, pilot clinical trial. Twenty-five subjects will be enrolled in order to have 20 subjects complete the study with roughly 10 subjects in each treatment regimen arm. Subjects will be randomly assigned in a 1:1 ratio to either Vitamin D3 (cholecalciferol) or metformin for 12 weeks. Evaluations will be completed at baseline, after 6 weeks, and after completing 12 weeks of treatment. Blood specimen collection and analysis will occur at baseline and after 12 weeks of treatment. Screening data will be reviewed to determine subject eligibility. Subjects who meet all inclusion criteria and none of the exclusion criteria will be entered into the study.

Total duration of subject participation will be 12 weeks. The following treatment regimens will be used:

- The Vitamin D group will receive 5,000 IU cholecalciferol (Vitamin D3) tabs once daily
- The Metformin group will receive 500 mg metformin once daily for the first week, 500 mg twice daily for the second week, and 1,000 mg twice daily for the duration of the 12-week trial.

Standard Survey Instruments

Beck Depression Inventory II (BDI-II),

State Trait Anxiety Inventory (STAI)

PCOS-related quality of life by the PCOS Quality of Life survey (PCOSQ)

International Physical Activity Questionnaire (IPAQ)

Blood specimen Assays

Blood specimens are assayed at Quest Diagnostics as part of routine clinical diagnostics, for participation in the UCSF PCOS Multidisciplinary clinic. This is a requirement for initial clinic intake, and the panel is

routinely repeated again after 3 months as part of clinical follow-up. These specimens are not stored but rather discarded after assay.

For those Clinic patients who did not have specimens assayed at Quest initially for these clinical baseline purposes, we will repeat the panel testing at Quest Diagnostics for consistency of assays for research purposes. Specimens are destroyed after assay and are not stored.

Inclusion Criteria

1. Female age 18-45
2. Documentation of a Polycystic Ovary Syndrome diagnosis by Rotterdam Criteria
3. Insulin resistance as evidenced by HOMA-IR > 2.0, calculated from fasting glucose and insulin
4. Mild or greater severity depression as evidenced by BDI-II > 14
5. Written informed consent obtained from subject and ability for subject to comply with the requirements of the study.

Exclusion Criteria

1. Currently receiving pharmacologic treatment for depression

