Sample Size Calculations: In our study, the primary outcome is change in BDI-II score (depression symptoms). A 3-point difference in BDI-II change is considered clinically significant (38). We determined expected change in BDI-II scores and standard deviations from prior studies of Vitamin D (14) and metformin (39). Using an alpha=0.05, power=0.80, and a 1:1 randomization scheme, we calculated a sample size of 8 per group, for a total of 16. Given a level of uncertainty with our assumptions on the basis of limited prior research, we aim to have 10 subjects per group complete the trial, for a total of 20. Assuming 20% attrition, we will recruit 25 subjects to result with 20 in total.

Statistical Analysis Plan: The primary endpoint is to investigate the effectiveness of the treatments on the BDI depression scores. The secondary endpoints are the change in HOMA-IR and 25(OH)D. These models will be adjusted for important covariates as needed such as BMI, age and baseline BDI-II as appropriate. Summary statistics will be provided and all testing will be performed at the 0.05 level of significance. Exploratory analyses will test for a relationship between change in HOMA-IR and 25(OH)D and depression scores.

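### The plan does not specify the scale or an own-baseline term for the HOMA-IR secondary endpoint; log HOMA-IR adjusted for its baseline would be a cheap gain in efficiency

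*Combined protocol and SAP*

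**What the plan says.** The Statistical Analysis Plan section defines the endpoint in one sentence: "The secondary endpoints are the change in HOMA-IR and 25(OH)D". On modelling it adds: "These models will be adjusted for important covariates as needed such as BMI, age and baseline BDI-II as appropriate". On testing it says that "all testing will be performed at the 0.05 level of significance". It does not state a scale, a transformation or a test for HOMA-IR, or whether the comparison is between arms or within each arm.

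The Inclusion Criteria require "Insulin resistance as evidenced by HOMA-IR > 2.0, calculated from fasting glucose and insulin".

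The Blood specimen Assays text indicates that the clinic intake panel supplies the baseline value, and that the panel is repeated for women whose intake samples were not run at the study laboratory. The Project Summary lists HOMA-IR at baseline, 6 weeks and completion, whereas Design & Methods has blood drawn only at baseline and 12 weeks. Both include week 12.

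Standard Clinical Practices says that every patient is counselled on diet and exercise, and treats this as an intervention against insulin resistance.

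**The concern.** HOMA-IR is calculated from fasting insulin and glucose, so it cannot be negative and usually has a long right tail. The entry threshold adds a floor at baseline. On the raw scale, women with high baseline values have the largest absolute changes, both by chance and under a proportional effect. With 10 women per arm, a few of them can dominate the mean change and its standard error.

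A separate issue is that women are selected for a high HOMA-IR. Where the qualifying sample is also the baseline, part of the later fall is regression to the mean.

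The hypothesis is that treating insulin resistance or vitamin D deficiency improves mood, and HOMA-IR change bears on whether insulin resistance was in fact treated. At stake are a real effect on HOMA-IR that goes undetected, and a fall within one arm that is credited to the drug. The Primary Aims are worded arm by arm and there is no untreated arm, so the second reading would come easily.

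**Working it through.** **The plan's own figures.** The plan states: "we aim to have 10 subjects per group complete the trial, for a total of 20". It also states: "Assuming 20% attrition, we will recruit 25 subjects to result with 20 in total". The recruitment figure reproduces: 20 / (1 − 0.20) = 25. The power calculation concerns BDI-II only. There is no HOMA-IR power, SD, correlation or expected effect to reproduce, so all sizes below rest on stated assumptions.

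**First set of assumptions.** HOMA-IR is lognormal with population median 3.0, between-woman log-SD 0.4 to 0.8 and within-woman log-SD 0.2 to 0.3. Women are enrolled if the observed value exceeds 2.0. There are 10 completers per arm, two-sided alpha is 0.05, and one arm falls by 30% while the other does not change. Simulated power (5,000 trials per setting):

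| Between / within log-SD | Raw change, t-test | Raw, own baseline | Log, own log baseline | Gain, log model over raw change |
|---|---|---|---|---|
| 0.4 / 0.2 | 62% | 72% | 78% | 16 |
| 0.4 / 0.3 | 33% | 43% | 47% | 14 |
| 0.6 / 0.2 | 56% | 66% | 75% | 19 |
| 0.6 / 0.3 | 31% | 38% | 45% | 14 |
| 0.8 / 0.2 | 50% | 60% | 73% | 23 |
| 0.8 / 0.3 | 28% | 33% | 43% | 15 |

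Repeat runs gave gains of 14 to 25 points. Type I error of the log model was about 5%.

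**Changing only the effect.** A 20% fall against none gives a gain of about 5 to 12 points. A 30% fall against a 15% fall in the comparator gives about 6 to 16.

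**Wider assumptions.** A second simulation covered 128 scenarios: median 2.5 or 3.5, log-SD 0.4 to 0.7, correlation between visits 0.5 to 0.8, and between-arm ratio 0.8, 0.7, 0.6 or 0.5. The log model with own baseline was ahead in all 128, by 1 to 34 points (median 14). By ratio, the gain was 3 to 10 (0.8), 9 to 18 (0.7), 5 to 26 (0.6) and 1 to 34 (0.5).

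**Where the gain comes from.** In one scenario of the second set (median 3.5, log-SD 0.6, correlation 0.6, ratio 0.6), power was 35% for raw change, 50% for raw with own baseline, 54% for log change and 58% for log with own baseline. Taking logs alone gives 54 − 35 = 19 of the 58 − 35 = 23 points. Own baseline then adds 4 points on the log scale, against 50 − 35 = 15 on the raw scale. Across the second set, own baseline changed power on the log scale by about −1 to +7 points.

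**Bias.** With no treatment effect, the between-arm test on raw change rejects in 4.5% to 4.6% of trials in the second set. The randomised comparison is valid.

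**Fall from selection alone.** If the qualifying sample is the baseline, let s be the total log-SD, ρ the correlation between visits and a = (ln 2 − ln median) / s. The expected log change without treatment is −(1 − ρ) × s × φ(a) / [1 − Φ(a)].

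- Median 3.0, log-SDs 0.4 and 0.3: s = √(0.16 + 0.09) = 0.50, ρ = 0.16 / 0.25 = 0.64, a = −0.405 / 0.50 = −0.81, ratio φ/(1 − Φ) = 0.363. Log change = −0.36 × 0.50 × 0.363 = −0.065, a fall of 6.3% in geometric mean.
- Median 3.0, log-SDs 0.8 and 0.2: s = √(0.64 + 0.04) = 0.825, ρ = 0.64 / 0.68 = 0.941, a = −0.49, ratio 0.513. Log change = −0.059 × 0.825 × 0.513 = −0.025, a fall of 2.5%.

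The first set as a whole gives about 2% to 7%. In the second set the fall in mean raw HOMA-IR is about 1% to 12%, and a paired test in one arm shows a significant fall in about 3% to 10% of trials against 2.5% nominal. With a separate baseline sample, the expected fall is 0.00.

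**The case against.** **The power figure is not a property of this trial.** This stands. Every input for HOMA-IR is assumed. A comparator that does not change favours the claimed gain, because the documents give both arms diet and exercise counselling and mention a possible, unproven insulin-sensitising role for vitamin D in diabetics. In the wider grid, 61 of 128 scenarios gave a gain below 14 points. A reader might infer one fixed power loss from the first table; the documents do not support that.

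**The plan does not exclude own baseline.** This stands. The covariate list is introduced by way of example and applied as needed. A reader might infer that HOMA-IR will be analysed without its baseline, but the text only leaves this open. Raw change is likewise the natural reading of the endpoint, not a stated analysis.

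**The gain bundles two changes.** This stands in part. If own baseline is already in the raw model, the log scale adds 4 to 13 points in the first table. The split depends on which step is taken first, but both steps are in the same model.

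**Regression to the mean is shared by the arms.** This stands. A reader might infer that selection at 2.0 biases the trial's HOMA-IR result. It does not bias the randomised contrast, and it disappears where a repeat panel serves as baseline. The plan also specifies no within-arm HOMA-IR test, so a misreading of a within-arm fall is a risk and not a planned analysis.

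**The endpoint is secondary, in a pilot, and unpowered.** This stands and limits the weight of the point. In half the settings of the first table, even the better model reaches only 43% to 47% power. It does not argue against a change that needs no extra data.

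**Conclusion.** The point holds as a cheap improvement to an unpowered secondary endpoint. The plan leaves the scale and the own-baseline term for HOMA-IR unspecified, and raw change was the less efficient choice in every setting with a treatment effect that was tried. If HOMA-IR is lognormal and one arm falls by 30% against none, the gain is about 14 to 25 power points. It is about 5 to 16 for a 20% fall or a 15% fall in the comparator, and 1 to 34 over wider inputs. Most of it comes from the log scale; own-baseline adjustment helps mainly on the raw scale. No figure was computed for 25(OH)D.

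The documents do not support calling the planned comparison biased or its type I error inflated. The narrower statement that holds is that a fall within one arm is not evidence of drug effect. Where the qualifying sample is the baseline, selection alone lowers HOMA-IR by roughly 2% to 7% (geometric mean, first set of assumptions) in both arms, and lifestyle counselling could lower it further.

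**What to change.** Amend the Statistical Analysis Plan section as follows:

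- **HOMA-IR:** regress week-12 log HOMA-IR on arm and log baseline HOMA-IR, and report the between-arm ratio of geometric means with its confidence interval.
- **25(OH)D:** adjust the between-arm comparison for baseline 25(OH)D.
- **Within-arm HOMA-IR change:** report as descriptive only, with no test.
- **Baseline sample:** state which sample is the baseline when a panel has been repeated.

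The cost is SAP wording only. The baseline and week-12 values are already collected, and no visits, samples or subjects are added. The small downside is that HOMA-IR results read as ratios and not in HOMA-IR units.
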